7.2.5. Potential Risks of Measuring Flow Mediated Dilation with Brachial Artery Ultrasound

There are no significant risks associated with ultrasound imaging of the brachial artery, or with the 5 minutes of reduced blood flow that is part of the test. Cutting off blood flow to the arm may result in mild discomfort or temporary sensations of tingling or numbness in the hand until the blood pressure cuff is released. About 1 in 200 patients develop a painless rash on the arm where the blood pressure cuff is placed; this disappears over several days.

7.2.6. Potential Risks of Measuring Left Ventricular Strain

There are no significant risks associated with ultrasound imaging to measure left ventricular strain.

7.2.7. Potential Risks associated with other study procedures

Bruising during the venipuncture and vasovagal response to phlebotomy are the anticipated risks of venipuncture. There are no anticipated risks for completion of questionnaires or collection of a urine sample from female subjects. Light bicycle exercise (used to increase minute ventilation) presents a potential, but minimal risk. Side effects of exercise include occasional muscle soreness, cramps or general fatigue. These effects are temporary and not typically harmful to volunteers. It is also possible that exercise might uncover a previously unidentified pre-existing cardiac condition that could present a health risk to a volunteer.

Additionally there is a risk of Breach of Confidentiality and Privacy.

7.3. Measures to Minimize Risk

7.3.1. Protections to Minimize Risk of Gamma Tocopherol

Tocopherols may affect coagulation. We will query volunteers for bruising and bleeding prior to enrollment and during the dosing period, and will monitor PT and aPTT values prior to the first dose of study drug and at the end of the dosing period. They may be checked at any time the subjects experiences abnormal bruising. Any participant with an abnormal baseline PT, aPTT or INR will be excluded from receipt of study treatment. Spirometry is performed at regular intervals throughout the γ T dosing period to monitor for any changes in lung function. As to the incidence of gastrointestinal symptoms, we will recommend that γ T supplements be taken with a high-fat meal to promote intestinal absorption of γ T and mitigate many associated diarrhea or bloating. Participants will receive a GI symptom diary to be completed daily while taking the study drug and returned to study coordinators on the morning of the challenge visits (Visit 2 or 5). All female subjects, except those who have had a hysterectomy with oophorectomy, will undergo urine pregnancy testing prior to beginning treatment and prior to WSP exposure. A positive pregnancy test will exclude the subject, and they will be withdrawn if they become pregnant during the course of the study. Study medication, including placebo, will be dispensed by the Investigational Drug Service of UNC Hospitals.

7.3.2. Protections to Minimize Risk of Wood smoke exposure

Prior to enrollment, subjects will have completed either the CEMALB screening protocol at which time a detailed medical history will be obtained. Only otherwise healthy volunteers who meet study inclusion/exclusion criteria will be considered for this study, and the maximum age of participants will be 45 years in order to limit the likelihood of occult disease. Subjects will be deferred if they have had a viral upper respiratory tract infection within 4 weeks of exposure challenge. Also, unspecified illnesses, which in the judgment of the investigator increase the risks associated with woodsmoke, will be a basis for exclusion. All subjects will need to fulfill objective lung function and symptom criteria outlined above in section 3.4.1. prior to chamber entry. During wood smoke exposure, subjects will be monitored by direct observation or via closed-circuit television. Subjects will have ECG telemetry leads attached to monitor cardiac rate and rhythm during exercise throughout the exposure. Subjects will be aware that they can

terminate their exposure for any reason and still receive compensation for their participation up to that point. A physician familiar with the protocol will be available for all challenge procedures. The investigator or duty physician will end the exposure if the subject is found to be suffering from any major adverse effect. An emergency “crash cart” with standard emergency medications, IV fluids and a defibrillator are also readily available at the CEMALB in the unlikely event of a medical emergency during any challenge or study visit.

For safety reasons, pulse oximetry will be performed during the exposures to wood smoke and filtered air, and the subject will be withdrawn from the chamber if the value is <90%. The risk of discomfort associated with exercise will be limited because ability and response to exercise will be assessed at the training visit, and subjects with orthopedic issues that limit ability to pedal a bicycle will be excluded. All female subjects, except those who have had a hysterectomy with oophorectomy, will undergo urine pregnancy testing on the morning (prior to) of each exposure. A positive pregnancy test will exclude the subject. Various engineering system controls will be used during woodsmoke exposures. A Tapered Element Oscillating Microbalance (TEOM®) will be used control and monitor wood smoke particle concentration in the chamber. If the concentration measured by the TEOM® exceeds a predetermined level, the exposure will be terminated and the subject removed from the chamber. A DataRAMTM particulate measurement device will also be used during exposure as an alternative monitor for independent verification of proper TEOM® operation. Additionally, gas analyzers continually monitor the chamber environment during exposures and will alarm if the carbon monoxide level exceeds 35 ppm.

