3.4.1. Criteria for safety prior to initiation of wood smoke inhalation challenge

(Subjects not meeting these criteria the morning of challenge will not proceed with wood smoke inhalation challenge):

1. FEV₁ of at least 75% of predicted (without use of bronchodilating medications for 12 hours) consistent with lung function of persons with no more than mild intermittent or mild persistent asthma.
2. Baseline oxygen saturation of at least 93%.
3. No history of viral respiratory tract symptoms within 4 weeks of challenge.
4. No current symptoms of rhinorrhea, sneezing, nasal or ocular pruritus consistent with allergic rhinoconjunctivitis.

3.4.2. Criteria for safety of a given individual following challenge which would suspend the individual from further participation in the study will include:

1. No greater than 25% relative decrease in FEV₁ or FVC from WSP pre-challenge values, which does not improve within the first 2 hours of challenge.
2. FEV₁ must recover without treatment to within 90 % of baseline within 24 hours.
3. A symptom score no greater than 45 (representing a ranking of “moderate” on each of 15 criteria, with a maximum score of 60, see section 5.2.8. below) with improvement to a score of 15 or less within 6 hours without therapy.
4. Specifically, no symptom score greater than “moderate” (3 on a scale of 0-4) for shortness of breath or cough at 24 hours post-challenge.
5. Oxygen saturation of $\geq 93\%$ throughout the exposure period.
6. If albuterol therapy is needed more than once during an observation period.
7. Any significant abnormalities in PT and aPTT during the treatment periods will be assessed and reported to CDER, IRB, and the funding agency.

Criteria for safety within the entire protocol (failure of which would result in suspension of further study until consultation with the CDER of the FDA and the UNC IRB) will include the following:

1. The study will be suspended if 3 of the first 10 participants fail the individual safety criteria outlined above. If this occurs, the study will remain suspended until consultation with the CDER of the FDA.
2. Once 10 subjects have been enrolled, study suspension will occur if more than 25% of all participants fail the individual safety criteria outlined above
3. No occurrence of any SAE

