Subjects will be under direct supervision for 6 hours from the start of WSP challenge and will have contact information for after-hours access to a study physician. In the event of an unexpected event, such as wheezing or bronchospasm, the physician will follow the usual medical standard of care to treat the subject.

4. Subject Selection and Withdrawal

Preliminary results from our screening WSP exposure study have shown that approximately 57% of healthy volunteers were responsive to the inflammatory effects of WSP. Based on this experience, we estimate we will need to screen 50 volunteers to identify 28 who are responsive to inhaled WSP. Anticipating an attrition rate of 20%, we will need to identify 35 volunteers for the intervention study, requiring an overall screen of a minimum of 64 volunteers. There will be no gender or ethnic restrictions. The target completion goal is 28 healthy volunteers and mild asthmatics. Individuals who meet all of the following criteria are eligible for enrollment as study participants.

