4.3. Withdrawal or Termination

Participants will be terminated early from the study for the following reasons:

1. The participant elects to withdraw consent from all future study activities including follow up.
2. The participant is “lost to follow up” (i.e., no further follow up is possible because attempts to reestablish contact with the participant have failed).
3. The participant dies.
4. The participant develops a medical condition or is started on a new medication(s) not previously mentioned in the list of prohibited medications that, in the opinion of the investigator, may pose additional risks from participation in the study, may interfere with the participant’s ability to comply with study requirements or that may impact the quality of the data obtained from the study.
5. The participant meets any of the individual stopping rules as delineated.
6. The study is terminated for any reason.

Participants with early termination from this study will not be replaced.

5. Study Procedures

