7.1. Definition of Adverse Event (AE) and Serious Adverse Event (SAE)

Adverse events and serious adverse events will be recorded and reported according to 21 CFR 312.32. An adverse event for a given volunteer will be defined as any untoward medical occurrence associated with the use of a drug whether or not considered drug related and will also include failure of any of the safety criteria outlined in section “3.4.”. Additionally, minor upper respiratory tract infections occurring within 96 hours of the exposure will be considered adverse events. Other non-specified clinical illnesses or symptoms, which occur during the treatment period or within 96 hours of each challenge, will also be reported as an AE. Any decrease in lung function or increase in symptom score, as outlined in section “3.4,” will be considered an

adverse event. Any symptoms that induce a volunteer to seek medical attention from any provider during study drug treatment or within 7 days of completing study drug treatment or within 96 hours of challenge will be considered an adverse event. A serious adverse event will also be defined as any event that requires hospitalization or results in life threatening illness or injury, permanent (or likely to be permanent) illness or injury, or death if these events occur during study drug treatment or within 7 days of completing study drug treatment or within 96 hours of challenge (or if the clinical scenario leading up to hospitalization, illness, injury or death begins during study drug treatment, within 7 days of completing study drug treatment or within 96 hours of a challenge).

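### Section 7.3.2 removes a participant from the chamber only below 90% saturation, although a reading below 93% bars entry and already fails a participation-ending safety criterion

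*Combined protocol and SAP*

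**What the plan says.** Five parts of the protocol bear on oxygen saturation around the exposure.

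- **Entry (3.4.1 item 2).** The challenge does not start unless the participant has "Baseline oxygen saturation of at least 93" (percent) that morning.
- **During exposure (3.4.2 item 5).** Saturation must be at least 93% "throughout the exposure period". The lead-in describes the list as criteria for the individual "following challenge which would suspend the individual from further participation in the study".
- **Termination (4.3 item 5).** A listed reason for early termination is: "The participant meets any of the individual stopping rules as delineated".
- **Adverse events (7.1).** The definition "will also include failure of any of the safety criteria outlined in section" 3.4, so a reading below 93% in the chamber is also an adverse event.
- **Removal from the chamber (7.3.2).** Pulse oximetry is performed during exposures, and "the subject will be withdrawn from the chamber if the value is <90" (percent).

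Other protections do not depend on a saturation value. "Subjects will be under direct supervision for 6 hours from the start of WSP challenge", and participants are watched directly or by closed-circuit television with ECG telemetry. They may stop at will. "The investigator or duty physician will end the exposure if the subject is found to be suffering from any major adverse effect". Excess particle concentration also ends the session.

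**The concern.** A participant at 92% on the morning of challenge may not enter the chamber. The same participant at 92% while cycling in wood smoke has failed a criterion that ends participation in the study, but no saturation rule takes them out of the smoke until the reading falls below 90%. The stricter limit therefore applies before exposure, and again when study status is decided, but not to the session in progress.

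The exposure has no therapeutic purpose (the exclusion criteria in 4.2 describe the protocol as non-therapeutic). Participants may have mild asthma, and section 7.2.2 acknowledges that they may have more airway inflammation after exposure. Nothing is gained for the participant by finishing a session once the criterion has failed. Staff who apply 7.3.2 literally would continue, while staff who take 3.4.2 and 4.3 to cover the rest of the session would stop. What is at stake is participant safety and consistent handling of the same reading, not the statistical conclusions.

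**Working it through.** There is no plan figure to reproduce. The check compares the limits and counts where they apply.

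**1. Limits side by side** (assuming whole-number readings)

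| Reading | Entry, 3.4.1 | In-exposure criterion, 3.4.2 item 5 | Removal, 7.3.2 |
|---|---|---|---|
| 93% or above | may enter | met | not required |
| 90, 91, 92% | may not enter | failed | not required |
| 89% or below | may not enter | failed | required |

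The middle row holds three readings: 90, 91 and 92.

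**2. Distance between the two limits.** For a participant entering at saturation B, the criterion fails after a fall of B − 92 points, and removal is required after a fall of B − 89. The gap is (B − 89) − (B − 92) = 3 points, whatever B is. At the entry minimum, B = 93, a fall of 93 − 92 = 1 point fails the criterion and a fall of 93 − 89 = 4 points forces removal.

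**3. Does any other text cover the middle row?** Section 7.3.2 refers back to 3.4.1 for chamber entry but not to 3.4.2. Section 4.3 item 5 concerns termination from the study and does not mention the session under way. The physician stop needs a major adverse effect, with no saturation value attached. The particle stop depends on chamber concentration. No text links 93% with 90% or gives a chamber action between them.

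**4. Is the failure visible while the session runs?** Yes. Most items in 3.4.2 are judged hours after challenge, but item 5 is worded for the exposure period itself, and 7.3.2 already provides oximetry during it.

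**5. Exposures governed by the rule.** There is one wood smoke exposure per period and there are two periods (5.1.4). With the completion target of 28 (section 4), 28 × 2 = 56. With all 35 enrolled participants completing both periods (6.1), 35 × 2 = 70. This counts where the rule applies. It does not estimate how many sessions would have a reading of 90 to 92%, and the documents give no such frequency.

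**6. What earlier removal would do to the endpoint.** The primary endpoint uses sputum at 4 and 24 hours after exposure (3.2). Removal shortens the 2-hour exposure and so lowers the delivered dose for that period. The affected participants are those whom 3.4.2 already suspends. If the failure is in period 1, the suspension already rules out period 2, so their within-person comparison is lost under the present text too. If it is in period 2, the added effect is confined to that period's 4-hour and 24-hour samples.

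**The case against.** The strongest reply is that each limit already has its own action. Below 93% the participant fails a criterion and leaves the study; below 90% the participant leaves the chamber. The lead-in to 3.4.2 speaks of the individual after challenge and of participation in the study, most of its items are judged later, and 7.3.2 is the specific in-chamber rule. The protocol does something similar with lung function: 7.2.2 gives rescue albuterol for an FEV1 fall of 20% or more immediately after exposure, while 3.4.2 item 1 uses a 25% fall that does not improve. That reading is coherent and may be the more natural one.

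A reader might therefore infer too much in either of two directions.

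- **That the sections contradict each other.** They do not. The limits trigger different actions and both can be obeyed at once.
- **That participants at 90–92% are unprotected, or have been harmed.** Supervision, telemetry, the physician stop and the right to leave all remain. Participants are 18–45 with FEV1 at least 75% of predicted, and all have already been through a screening wood smoke exposure. The documents report no reading in this band.

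What survives is narrower. Even on the two-tier reading, someone who could not have entered the chamber at that saturation, and whose participation has just ended, may stay in the smoke. A sentence declaring two tiers would remove the ambiguity but leave that result in place.

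The objection is also right that pausing or ending an exposure departs from the standardised dose and can affect the primary sputum measure. That cost belongs in the decision.

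**Conclusion.** The point holds as a minor safety misalignment and is best labelled a cheap improvement. The removal limit in 7.3.2 sits 3 points below the limit that 3.4.1 and 3.4.2 already treat as unacceptable. It leaves readings of 90, 91 and 92% with a failed participation-ending criterion and no required removal, across a planned 56 to 70 exposures.

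This rests on reading 3.4.2 item 5 literally, so that any reading below 93% during exposure is a failure, and on oximeters reporting whole numbers. It does not rest on any assumed frequency; the number of sessions affected is unknown and could be zero.

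It would be wrong to infer a statistical flaw. The power calculation in 6.1 and the analysis in 6.2 do not depend on the saturation limit.

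**What to change.** In 7.3.2, replace the removal limit of below 90% with two steps:

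- A reading below 93% during exposure is rechecked immediately. If the recheck is also below 93%, the participant is removed from the chamber.
- A reading below 90% means immediate removal, without a recheck.

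The entry limit in 3.4.1 and the consequences in 3.4.2, 4.3 and 7.1 stay as they are. The change brings the chamber instruction into line with them.

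**Cost.** It takes a line or two of protocol text and one step in the chamber procedure. Oximetry is already in place, so there is no new measurement. The real downside is to the exposure: a recheck may briefly interrupt a session, and a confirmed reading ends it, which changes the delivered dose and may alter or lose that period's 4-hour and 24-hour sputum values. Early ending is limited to participants whom 3.4.2 already suspends. Interruptions and shortened exposures should be recorded with their timing so that the affected samples can be identified at analysis.

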7.3.3. Protections to Minimize Risks of the Induced Sputum Procedure

Throat irritation will be minimized by providing the subject with a drink (water, juice etc) and a snack after induction. All subjects with a history of asthma will be pretreated with 2-4 puffs of albuterol prior to procedure initiation. An additional albuterol multidose inhaler will be immediately available in the event the subject experiences symptoms of bronchoconstriction. A physician on duty in the facility will be available during sputum inductions. If the covering physician feels that the subject's respiratory status is such that providing an induced sputum sample would place them at increased risk for significant bronchospasm, sputum sampling will be deferred. Baseline FEV₁ and force vital capacity (FVC) will be measured before the start of the induction and at the end of each level (concentration) of saline inhalation. The FEV₁ values that match a 10% and 20% reduction from baseline will be calculated and recorded. Subjects who have a 10-20% decrease in FEV₁ after the 3% or 4% level of saline will not be advanced to a higher concentration of saline and will continue at the same level. If the FEV₁ drops by > 20%, the induction will be stopped and the subject will be treated with 2 puffs of albuterol. Additional albuterol may be given if needed.

7.3.4. Protections to Minimize Risks of Spirometry

Subjects will be seated in a non-rolling chair when spirometry is performed and standard methodology conforming to the American Thoracic Society guidelines for measurement of spirometry will be used. Subjects will be instructed to notify the study staff if they feel lightheaded, and albuterol will be available in the event the subject experiences any unanticipated bronchoconstriction.

7.3.5. Protection to Minimize Risks Associated with FMD

If any subject finds this procedure intolerable, he or she will be withdrawn. In the rare event of a rash in the area where circulation is restricted, the subject will be monitored until it resolves.

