3.2. Primary Study Endpoint

The primary endpoint will be change in sputum %PMNs [Δ (postWSP (4 hr) – preWSP)[γ T] vs Δ (postWSP (4 hr) – preWSP)[placebo]] and change in sputum %PMNs [Δ (postWSP (24 hr) – preWSP)[γ T] vs Δ (postWSP (24 hr) – preWSP)[placebo]].

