3.3. Secondary Study Endpoints

The secondary endpoints of the study will be change in peripheral blood absolute neutrophil count (ANC) in cells $\times 10^9/L$ [Δ (postWSP (4 hr) – preWSP)[γ T] vs Δ (postWSP (4 hr) – preWSP)[placebo]] and [Δ (postWSP (24 hr) – preWSP)[γ T] vs Δ (postWSP (24 hr) – preWSP)[placebo]].

Exploratory endpoints of interest include:

1. Role of asthma as a modifier of γ T treatment effect on WSP-induced airway inflammation
2. Spirometry measurements – forced vital capacity (FVC), forced expiratory volume in 1 second (FEV₁), FEV₁/FVC ratio
3. Secretion of sputum mucins (total sputum mucins, MUC5AC, MUC5B) will be determined by Western blot
4. Serum cytokine concentrations via Mesoscale:
 - a. TH1 cytokines: IL-1b, IL-6, IL-8, TNFa
5. Sputum cytokine concentrations via Mesoscale:
 - a. TH1 cytokines: IL-1b, IL-6, IL-8, TNFa
6. Flow mediated dilation (FMD) using brachial artery ultrasound
7. Left ventricular strain (LVS)
8. Serum concentrations of gT aT gCEHC and aCEHC.

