5.1.4. Visits 2 (Period 1) and 5 (Period 2): WSP exposure

1. Vital signs, oxygen saturation, resting blood pressure
2. GI and WSP Exposure symptom questionnaire
3. Collect symptom diary
4. Urine pregnancy test for females
5. HRV will be collected throughout the entire visit with a Spacelabs monitor. The monitor will be worn until the 24 hours post exposure visit.
6. Spirometry
7. Venipuncture (CBC with differential, serum cytokines, serum C-reactive peptide, lipid panel, LDH, fibrinogen, gT and metabolite levels)
8. 500 μ g/m³ WSP chamber exposure for 2 hours, with intermittent exercise and rest. Subjects will alternate 15 minutes of exercise on a cycle ergometer (intensity needed to achieve 20 L/min/m² BSA determined at baseline visit) with 15 minutes of rest.
9. Symptom questionnaire (immediately prior to exit from the chamber)
10. Spirometry and resting blood pressure (immediately following exit from the chamber)
11. Lunch - low fat meal is provided. The meal must be the same during each exposure.
12. Obtain 30 minute controlled rest HRV, FMD, and LVS (90 minutes post-WSP exposure)

13. Venipuncture (CBC with differential, serum cytokines, serum C-reactive peptide, lipid panel, LDH, fibrinogen) (4 hours post-WSP exposure)
14. GI and WSP Exposure Symptom questionnaire (4 hours post-WSP exposure)
15. Sputum induction (4 hours post-WSP exposure)

5.1.5. Visit 4: Dispense Study Drug (Period 2) (following 4 week washout and at least 1 week prior to V5 Exposure Visit and up to 3 weeks)

1. Review medical history and adverse events
2. Urine pregnancy
3. Vital signs, oxygen saturation, GI symptom questionnaire
4. Dispense study drug
5. Lung function testing for participants who have asthma

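### As written, intolerance of an exploratory vascular or cardiac ultrasound withdraws the participant, and can do so before the primary post-exposure sputum is collected

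*Combined protocol and SAP*

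**What the plan says.** Section 7.3.5 (FMD) states "If any subject finds this procedure intolerable, he or she will be withdrawn". Section 7.3.6 (LVS) uses the same sentence. Neither section offers the choice of dropping the measurement alone.

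Section 3.3 lists "Flow mediated dilation (FMD) using brachial artery ultrasound" and LVS as exploratory endpoints 6 and 7. Section 3.2 says "The primary endpoint will be change in sputum %PMNs", assessed at 4 h and at 24 h after exposure. The secondary endpoint is the change in blood neutrophil count at the same two times.

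Both ultrasound measurements are made at V1 (section 5.1.3) and again at V2 and V5, where section 5.1.4 has "Obtain 30 minute controlled rest HRV, FMD, and LVS (90 minutes post-WSP exposure". The 4 h blood and sputum come later on the same day, and the 24 h samples come at V3 or V6.

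Section 4.3 gives six reasons for early termination and adds "Participants with early termination from this study will not be replaced". Intolerance of a procedure is not among the six. The fifth reason refers to individual stopping rules; the individual criteria in section 3.4.2 do not mention FMD or LVS.

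**The concern.** The sentence in 7.3.5 and 7.3.6 acts on the person, not on the measurement. A participant who has been randomised, has taken seven days of capsules and has completed the two-hour smoke exposure could be removed for not tolerating an arm cuff or an echocardiogram, shortly before the sample that carries the primary endpoint. The primary comparison is within person, so it needs post-exposure sputum from both periods. Losing that for the sake of an exploratory measurement is a poor exchange.

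The rule also does not fit with section 4.3, which is where a reader would look for the reasons that end participation. Staff following 7.3.5 and staff following 4.3 could act differently on the same event.

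**Working it through.** **Order of events.** Section 3.1 places randomisation before V0 and V1, so every FMD or LVS session follows it.

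| Session | What comes before | What a literal withdrawal loses |
|---|---|---|
| V1 | Randomisation and V0 baseline sputum; drug not yet dispensed (FMD and LVS are items 5 and 6, dispensing is item 8) | All post-exposure sputum and blood, both periods |
| V2, 90 min after exposure | Period 1 dosing and smoke exposure | 4 h and 24 h sputum and blood, both periods |
| V5, 90 min after exposure | Complete Period 1 data; Period 2 dosing and exposure | 4 h and 24 h sputum and blood of Period 2, and so the within-person difference |

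At V2 and V5 the gap between the ultrasound and the first primary sample is 240 − 90 = 150 minutes.

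**The plan's sample size, reproduced.** Inputs from section 6.1: effect 14.5, SD 25.9 (taken as the SD of the within-person difference), two-sided α 0.05, power 0.80 (the plan's β = 0.8 read as power).
- Normal approximation: (1.960 + 0.842)² × (25.9/14.5)² = 25.04, so 26.
- Exact paired t-test: at n = 28 the noncentrality is (14.5/25.9) × √28 = 2.96 and power is 0.815; n = 27 gives 0.7996. The smallest n reaching 0.80 is 28, as stated.
- Enrolment: 28/(1 − 0.20) = 35, using the 20% attrition in section 4. The allowance is 35 − 28 = 7 people. Section 6.1 gives 25% instead; at that rate 35 × 0.75 = 26.25 would complete.

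**What further losses would cost.** With a ordinary dropouts and w ultrasound withdrawals, completers = 35 − a − w. While a + w is at most 7, there are still at least 28 completers and nothing is lost against plan. If ordinary dropout has already used all 7:

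| w | Completers | Power (exact paired t) | SE relative to 28 |
|---|---|---|---|
| 0 | 28 | 0.815 | 1 |
| 1 | 27 | 0.800 | √(28/27) = 1.018 |
| 2 | 26 | 0.783 | √(28/26) = 1.038 |
| 3 | 25 | 0.766 | √(28/25) = 1.058 |

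**How often.** The documents give no intolerance rate. Assuming a rate p per participant over the whole study, expected withdrawals are 35p and the chance of at least one is 1 − (1 − p)³⁵:

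| Assumed p | Expected withdrawals | Chance of at least one |
|---|---|---|
| 1% | 0.35 | 30% |
| 2% | 0.70 | 51% |
| 5% | 1.75 | 83% |
| 10% | 3.5 | 97% |

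These rates only show the range. Section 7.2.5 describes mild, temporary discomfort from the cuff and section 7.2.6 reports no significant risk from LVS, which points to the low end.

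**The case against.** The strongest reply is that the sentence may mean withdrawal from the procedure. Section 7.3.2 uses the same verb for removal from the chamber, while 7.3.1 appears to use it for removal from the study after a positive pregnancy test, so usage is mixed. The silence of section 4.3 also suggests that study termination was not intended, in which case the no-replacement rule would not apply. This stands as a doubt about intent. It does not remove the need to edit, because the sentence names the subject and offers no narrower course.

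A second reply is that V1 performs both measurements before any drug is dispensed, so someone who cannot bear the cuff would most likely be found then. This stands, and it makes loss at V2 or V5 the less likely case. A loss at V1 is still that of a randomised participant.

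Third, a participant lost at V5 keeps the Period 1 data, and section 6.2 plans a random-effects model and multiple imputation, so those data need not be wasted. This stands in part: a paired test has no difference to use for that person.

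Fourth, the rule sits among the risk-minimisation measures, and a review should not prescribe continued dosing or exposure. This is accepted, and it limits the fix.

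Section 7.3.3 offers only a loose parallel. There, when a physician judges induction risky, "sputum sampling will be deferred" and the participant stays. But that is a judgement about bronchospasm, and deferring a fixed 4 h sample may lose that value too. It shows that the protocol can limit action to a procedure, no more.

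**Conclusion.** The point holds as a minor one. The wording of 7.3.5 and 7.3.6 allows primary and secondary data to be lost because an exploratory measurement was not tolerated, and it does not agree with the list in 4.3. The expected loss is small: probably few cases, most of them found at V1, and some or all absorbed by the seven-person allowance. The power figures above apply only if that allowance is otherwise used up, and they rest on 25.9 being the SD of the within-person difference.

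A reader might infer three stronger things. One is that the rule leaves the trial underpowered. The documents give no intolerance rate, and charging each withdrawal both to the allowance and to the 28 completers would count it twice. Another is that these are optional measurements. They are exploratory, but they are scheduled at three visits and nowhere called optional. The third is that such withdrawals have nothing to do with the drug or the smoke. At V2 and V5 they would arise 90 minutes after exposure, and the documents do not settle the cause.

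**What to change.** Reconcile 7.3.5 and 7.3.6 with 4.3. Word the two sentences so that what is withdrawn is the FMD or LVS measurement, with that exploratory value recorded as missing and the reason noted. State that intolerance of the measurement alone does not end collection of the 4 h and 24 h sputum and blood from a willing participant.

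Leave further dosing and exposure to the provisions already in the protocol: the individual safety criteria in 3.4.2, the reasons in 4.3 and the participant's consent. If the sponsor does intend withdrawal from the study, section 4.3 should list it as a reason, and the protocol should say whether the remaining post-exposure samples are still to be collected.

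The cost is one sentence in each of two sections and some missing FMD or LVS values, which withdrawal would lose anyway. This is a free improvement of minor severity.
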